### 4.11.1. Long-Term Efficacy Analyses

**Table JAHO4.9. Description of Analysis Between Week 36 and 104**

Measure	Variable	Analysis Method (Section 4.2.3)	Censoring Rule	Population (Section 4.2.1)	Time Point
Severity of Alopecia Tool (SALT)	Proportion of patients maintaining SALT $\leq 20$	Descriptive using NRI	Tertiary Plus Censoring	Randomized Withdrawal Population	Scheduled visits from Week 52 to 104
	Proportion of patients with SALT $\leq 10$	Descriptive using MI+NRI	Tertiary Plus Censoring		
	Proportion of patients regaining SALT $\leq 20$ after retreatment	Descriptive using NRI	Primary Censoring	Retreated Population	Summary statistics will be provided within 12, 16, 24, 36 weeks from retreatment
	Proportion of patients without loss of treatment benefit from Week 52	Descriptive using MI+NRI	Tertiary Plus Censoring	Randomized Withdrawal Population	Scheduled visits from Week 52 to 104
	Time to >20-point absolute worsening in SALT score from Week 52	Kaplan-Meier Plot		Retreated Population	
	Proportion of patients achieving SALT 50 /SALT 75 /SALT 90	Descriptive using NRI	Tertiary Plus Censoring	Randomized Withdrawal Population	Scheduled visits from Week 52 to 104
	Change or Percent change in SALT score	Descriptive using MI + mLOCF	Tertiary Plus Censoring	Randomized Withdrawal Population	Scheduled visits from Week 52 to 104

Measure	Variable	Analysis Method (Section 4.2.3)	Censoring Rule	Population (Section 4.2.1)	Time Point
PRO for Scalp Hair Assessment	Proportion of patients with a PRO for Scalp Hair Assessment score of 0 or 1 with a $\geq 2$ -point improvement from Baseline	Descriptive using NRI	Tertiary Plus Censoring	Randomized Withdrawal Population (among patients with a PRO for Scalp Hair Assessment score of $\geq 3$ at Baseline)	Scheduled visits from Week 52 to 104
ClinRO for EB Hair Loss	Proportion of patients with a ClinRO Measure for EB Hair Loss 0 or 1 with a $\geq 2$ -point improvement from Baseline;	Descriptive using NRI	Tertiary Plus Censoring	Randomized Withdrawal Population (among patients with ClinRO Measure for EB Hair Loss $\geq 2$ at Baseline)	Scheduled visits from Week 52 to 104
		Descriptive using MI+NRI	Tertiary Plus Censoring		
ClinRO for EB Hair Loss	Proportion of patients with a ClinRO Measure for EB Hair Loss 0	Descriptive using NRI	Tertiary Plus Censoring	Randomized Withdrawal Population (among patients with ClinRO Measure for EB Hair Loss $\geq 1$ at Baseline)	Scheduled visits from Week 52 to 104

Measure	Variable	Analysis Method (Section 4.2.3)	Censoring Rule	Population (Section 4.2.1)	Time Point
		Descriptive using MI+NRI			
ClinRO for EL Hair Loss	Proportion of patients with a ClinRO Measure for EL Hair Loss 0 or 1 with a $\geq 2$ -point improvement from Baseline	Descriptive using NRI	Tertiary Plus Censoring	Randomized Withdrawal Population (among patients with ClinRO Measure for EL Hair Loss $\geq 2$ at Baseline)	Scheduled visits from Week 52 to 104
		Descriptive using MI+NRI	Tertiary Plus Censoring		
ClinRO for EL Hair Loss	Proportion of patients with a ClinRO Measure for EL Hair Loss 0	Descriptive using NRI	Tertiary Plus Censoring	Randomized Withdrawal Population (among patients with ClinRO Measure for EL Hair Loss $\geq 1$ at Baseline)	Scheduled visits from Week 52 to 104
		Descriptive using MI+NRI	Tertiary Plus Censoring		

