Uptitration Population	All patients who are randomized to baricitinib 2-mg at baseline having SALT score >20 at Week 52 and were rescued to baricitinib 4-mg dose at Week 52. All patients need to take at least one dose of treatment and have non-missing SALT score on or after Week 52.
Retreated Population	A subset of patients who enter randomized withdrawal (randomized to placebo at Week 52) and were retreated with their baseline baricitinib dose at any time after experiencing loss of treatment benefit (SALT>20).
Safety Population	The safety population is defined as all randomized patients who receive at least 1 dose of investigational product (IP) and who did not discontinue from the study for the reason 'Lost to Follow-up' at the first postbaseline visit. Patients will be analyzed according to the IP to which they were assigned.

Abbreviations: AGA = androgenetic alopecia; GCP = good clinical practice; IP = investigational product.

a Some male patients with Grade IV AGA and female patients with patterned baldness may only be identified after hair regrowth on the scalp.

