#### **4.2.2. Definition of Baseline and Postbaseline Measures**

The baseline utilized in the efficacy analyses depends on the analysis being performed. The baseline value for the efficacy and health outcome analyses for all populations is defined as the last non-missing measurement on or prior to the date of first study drug administration (expected at Week 0, Visit 2) unless otherwise stated. If a patient is randomized but does not receive study drug, then the date of randomization is used instead of the first dose date. The efficacy and health outcome analyses for the randomized withdrawal population will use the measurement on or immediate prior to the date of Visit 2 (Week 0) or date of visit 11 (Week 52) as baseline as appropriate for the endpoints, unless otherwise stated. The efficacy and health outcome analyses for the retreated population will use the measurement on or prior to the date when patients got retreated.

Baseline for the safety analyses is defined as the last non-missing scheduled (planned) measurement on or prior to the date of first study drug administration for continuous measures by-visit analyses, unless otherwise stated, and all non-missing measurements on or prior to the date of first study drug administration for all other analyses.

Postbaseline measurements are collected after study drug administration through Week 200 (Visit 24) or early discontinuation visit. For data collected in the electronic Clinical Outcomes Assessment (eCOA) tablet (including Patient-Reported Outcomes [PRO] and Clinician-Reported Outcomes [ClinRO]) and related to efficacy assessments, unscheduled postbaseline visits that fall within the visit windows defined by Lilly will be summarized in the by-visit analyses if there is no scheduled visit available. Refer to clinical protocol I4V-MC-JAHO(e) for detail of the visit windows. If there is more than 1 unscheduled visit within the defined visit window and no scheduled visit is available, the unscheduled visit closest to the scheduled visit date will be used. If 2 unscheduled visits of equal distance are available, then the latter of the 2 will be used.

Postbaseline measures for the safety analyses are defined as the non-missing scheduled (planned) measurements after the date of first study drug administration for continuous measures by-visit analyses and all non-missing measurements after the date of first study drug administration for all other analyses.

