#### **4.4.1. Nonresponder Imputation**

For the analysis of categorical efficacy and health outcomes variables such as SALT  $\leq$  20 and PRO for Scalp Hair Assessment score of 0 or 1 with a  $\geq$ 2-point improvement from Baseline, the primary imputation method when an intercurrent event occurs will be nonresponder imputation (NRI), which can be justified based on the composite strategy ([ICH 2019]) for handling intercurrent events. This imputation procedure assumes that the effects of treatments disappear

after the occurrence of the intercurrent event. For analyses that utilize any of the censoring methods, randomized patients without at least 1 post-baseline observation will also be defined as nonresponders for all visits. As well, patients who are missing a value prior to discontinuation, rescue, dose change, or retreatment (if censoring on rescue or retreatment), i.e., the patient is missing an intermediate visit, will be imputed as nonresponders on that visit only.

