#### **4.17.3.3. Week 104 Interim Analysis**

After all randomized patients complete the efficacy assessment at Week 104 (Visit 18) or discontinue early, the database will be locked and data will be unblinded to a limited number of preidentified individuals to work on the interim analysis and authorize the scientific disclosures.

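### At the Week 104 lock, recapture after retreatment is summarised by NRI in all retreated patients, so follow-up not yet reached pulls the rate down, most at 36 weeks

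*SAP*

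**What the plan says.** The point rests on the SAP alone; the protocol supplied is the open-label addendum, which has no randomized withdrawal.

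- **Endpoint.** SAP Table JAHO.2.1 lists recapture of SALT ≤20 at 12, 16, 24 and 36 weeks of retreatment among the other secondary objectives, without multiplicity adjustment.
- **Analysis.** Table JAHO4.9 (SAP 4.11.1, Long-Term Efficacy Analyses) is titled "Description of Analysis Between Week 36 and 104". Its recapture row is "Descriptive using NRI" with the primary censoring rule, in the Retreated Population. The time point is "Summary statistics will be provided within 12, 16, 24, 36 weeks from retreatment".
- **Population.** Table JAHO.4.1 admits withdrawal patients randomized to placebo who "were retreated with their baseline baricitinib dose at any time after experiencing loss of treatment benefit". It sets no minimum follow-up.
- **Baseline.** SAP 4.2.2: "The efficacy and health outcome analyses for the retreated population will use the measurement on or prior to the date when patients got retreated".
- **NRI.** SAP 4.4.1 applies NRI when an intercurrent event occurs. It adds that "randomized patients without at least 1 post-baseline observation will also be defined as nonresponders for all visits".
- **Lock.** SAP 4.17.3.3: "After all randomized patients complete the efficacy assessment at Week 104 (Visit 18) or discontinue early, the database will be locked". Table JAHO4.9 does not name its lock, but its MI+NRI rows match the Week 104 method in SAP 4.4.5. SAP 4.2.1.1, by contrast, places retreated-population efficacy at the final lock.

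**The concern.** Withdrawal begins at Week 52 and relapse can be seen at any later visit, so retreatment dates run up to the cut. A window that has not elapsed is a different thing from a treatment failure. SAP 4.4.1 justifies NRI by assuming that the treatment effect vanishes after an intercurrent event; reaching a data cut is not an event in the patient, and the open-ended list in SAP 4.4 does not name it. Yet nothing takes such patients out of the denominator.

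The reported rate would then mix two things: whether retreatment works, and how late patients relapsed. The distortion grows with the window and flattens the later part of the recapture curve. According to SAP 4.17.3.3, the Week 104 analysis supports scientific disclosures. The group is also small, so a few misclassified patients matter.

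**Working it through.** The SAP gives no number retreated, no recapture rate and no share with full follow-up, so there is no planned figure to reproduce. The steps below show what follows from the documents and what needs assumptions.

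**1. Follow-up to Week 104.** Table JAHO.2.1 lists loss-of-benefit assessments at Weeks 64, 76, 88 and 104 (then 120 onward). If data stop at each patient's Week 104, follow-up = 104 − retreatment week:

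| Retreated at week | 64 | 76 | 88 | 104 |
|---|---|---|---|---|
| Weeks available | 40 | 28 | 16 | 0 |

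The latest retreatment week that allows a full window is 104 − window: 92, 88, 80 and 68 for 12, 16, 24 and 36 weeks. On this grid, only Week 64 retreatments complete 36 weeks.

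**2. How the rules classify patients.**
- *No assessment after retreatment:* with retreatment as baseline (4.2.2), the no-post-baseline rule in 4.4.1 makes them nonresponders in all windows.
- *Window partly elapsed, SALT ≤20 already regained:* recaptured, because *within* is cumulative.
- *Window partly elapsed, SALT ≤20 not yet regained:* no explicit rule. They are in the population, and an NRI row would most naturally count them as not recaptured.

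**3. Illustrative size (assumptions, not document figures).** Retreatment occurs only at the four weeks above. True cumulative recapture is 30/40/60/80% by 12/16/24/36 weeks, linear in between, so 28 weeks gives 60 + 20 × 4/12 = 66.7%. Three spreads over Weeks 64/76/88/104 are used: early 40/30/20/10%, even 25% each, late 10/20/30/40%. Reported rate = sum over visits of (share × recapture by the smaller of the window and the available follow-up).

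At 36 weeks:
- Early: 0.4×80 + 0.3×66.7 + 0.2×40 + 0.1×0 = 60%
- Even: (80 + 66.7 + 40 + 0)/4 = 47%
- Late: 0.1×80 + 0.2×66.7 + 0.3×40 + 0.4×0 = 33%

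| Window | Assumed true | Early | Even | Late |
|---|---|---|---|---|
| 12 wk | 30% | 27% | 22.5% | 18% |
| 16 wk | 40% | 36% | 30% | 24% |
| 24 wk | 60% | 50% | 40% | 30% |
| 36 wk | 80% | 60% | 47% | 33% |

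With straight-line accrual to 80% at 36 weeks instead, recapture is 80×28/36 = 62.2% by 28 weeks and 80×16/36 = 35.6% by 16 weeks. The 36-week figures become 58% (early), 44% (even) and 31% (late). Across both accrual shapes the range is about 31% to 60%, against a true 80%.

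**4. Scale.** SAP 4.1 expects about 100 patients in randomized withdrawal. SAP 3.1.2 allocates them 3:1 to baricitinib or placebo, so 100/4 = 25 could be retreated. If all 25 were retreated, each patient would be 1/25 = 4 percentage points.

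**The case against.** The strongest reply is that the SAP never says follow-up not yet reached is failure. NRI is tied to intercurrent events, and its missing-visit clause covers intermediate visits. On that view NRI is simply not triggered at a data cut. This stands in part: failure is explicit only for patients with no post-retreatment assessment, and even there one must read the retreatment baseline of 4.2.2 into 4.4.1. But no rule excludes or censors the others, so a programmer given an NRI row and this population has no instruction to remove them.

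Four further objections limit the point:
- **Cut-off.** The recapture row counts from retreatment and names no Week 104 limit. The lock waits for the last patient, and the retreated-population safety period in SAP 4.14 runs to the lock's cut-off date. Earlier enrollees may therefore have data after Week 104. The table title points the other way, so the efficacy cut is unstated. Later data would shrink the bias; late enrollees would still be truncated.
- **Visit grid.** Six numbered visits (12 to 17) lie between Week 52 (Visit 11) and Week 104 (Visit 18); the illustration uses three. Other retreatment dates would change the figures.
- **Final lock.** Tables JAHO.4.10 and JAHO.4.11 analyse the Retreated Population on observed data and by Kaplan-Meier time to SALT ≤20. That avoids NRI, although those rows do not list the 12- to 36-week windows.
- **Which lock.** If SAP 4.2.1.1 governs, this row may not belong to Week 104 at all. The final lock has its own retreated rows, however, so Table JAHO4.9 is hard to read that way.

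A reader might infer that every patient without a full window is scored a failure. In the example that would cut the 36-week figure to the share retreated at Week 64 × 80%, or 8% to 32%. The cumulative wording does not support this: recapture already seen counts.

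**Conclusion.** The concern holds for one descriptive, other-secondary row at the Week 104 lock. As written, the plan puts all retreated patients in every window's denominator under NRI, with no minimum follow-up and no stated efficacy cut-off. Wherever follow-up is truncated before recapture would have occurred, the bias is downward, and it is largest at 36 weeks.

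Its size cannot be derived from the documents. The 31% to 60% range depends on the assumed 80% true rate, the assumed accrual, the four-visit grid, the assumed retreatment spread and data stopping at Week 104. It illustrates direction and rough scale and is not an estimate of the trial's bias. Nor should a reader infer that the final recapture results are affected, since the final lock does not use NRI for this population.

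**What to change.** In Table JAHO4.9:
1. State the efficacy data cut-off for the recapture row.
2. For each window, include only patients whose retreatment date allows the full 12, 16, 24 or 36 weeks plus visit tolerance before that cut-off, and show that number. Alternatively, use a Kaplan-Meier estimate of time to SALT ≤20 from retreatment, censored at the cut-off, as already planned for the final lock.
3. Keep NRI for patients who discontinue or miss the visit within the window.
4. Reconcile SAP 4.2.1.1 with Table JAHO4.9 on which lock carries retreated-population efficacy.

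The SAP already uses this device: Appendix 1 defines Week 16 and Week 24 sensitivity sets limited to patients who would have completed that time by the interim lock.

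The cost is a short SAP clarification and re-tabulation, with no new data. The downside is small denominators. If all of about 25 placebo patients were retreated evenly over the four visits and data stop at Week 104, the 36-week window holds 25 × 25% ≈ 6 patients. Both options also assume that recapture does not depend on when retreatment began; under that assumption a true 80% is estimated as 80%.

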		SALT 100	Improvement in Baseline =100% % change from Baseline = -100	Missing if Baseline or observed value is missing

Measure	Description	Variable	Derivation/Comment	Imputation Approach if with Missing Components
		$SALT \leq 20$	Observed SALT score $\leq 20$	Missing if observed value is missing
		Absolute SALT score $\leq 10$	Observed SALT score $\leq 10$	Missing if observed value is missing
		Time to achieve $SALT \leq 20$	Date of visit for first time achieving $SALT \leq 20$ – randomization date at Visit 2	Censored at the last SALT collection date, scheduled visit date or ETV date during the blind treatment period, whichever is the latest and applicable
		With loss of treatment benefit in SALT from Week 52	Observed SALT score post Week 52 visit – observed SALT score at Week 52 $> 20$	Missing if any of these two observed values is missing.
		Without loss of treatment benefit in SALT from Week 52	Observed SALT score post Week 52 visit – observed SALT score at Week 52 $\leq 20$	Missing if any of these two observed values is missing.
Patient-Reported Outcome (PRO) for Scalp Hair Assessment	It's a novel patient-reported outcome (PRO) assessment of the patient's current extent of scalp involvement. Like the AA-IGA, it is comprised of 5 category response options: 0 = No missing hair (0% of my scalp is missing	PRO for Scalp Hair Assessment score	Single item. Range: 0 to 4	Single items, missing if missing.
		PRO for Scalp Hair Assessment score of 0 or 1	Observed score of 0 or 1	Single items, missing if missing.

Measure	Description	Variable	Derivation/Comment	Imputation Approach if with Missing Components
	hair; I have a full head of hair); 1 = A limited area (1%-20% of my scalp is missing hair); 2 = A moderate area (21%-49% of my scalp is missing hair); 3 = A large area (50%-94% of my scalp is missing hair); and 4 = Nearly all or all (95%-100% of my scalp is missing hair).	PRO for Scalp Hair Assessment score of 0 or 1 with a $\geq 2$ -point improvement from baseline	Observed score of 0 or 1 and change from baseline $\leq -2$	Missing if Baseline or observed value is missing.

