**Table JAHO.4.8. Description of Analysis Beyond Week 36 Placebo-Controlled Period**

Measure	Variable	Analysis Method (Section 4.2.3)	Population (Section 4.2.1)	Comparison/Time Point	Analysis Type
Severity of Alopecia Tool (SALT)	Proportion of patients maintaining SALT $\leq 20$	Descriptive	Randomized Withdrawal Population	Summary statistics will be provided at each post-baseline visit during the Long-Term Extension and Bridging Long-Term Extension Period	Other Secondary
	Proportion of patients with >20-point absolute worsening in SALT score	Descriptive	Randomized Withdrawal Population	Summary statistics will be provided at each post-baseline visit during the Long-Term Extension and Bridging Long-Term Extension Period	Other Secondary
	Time to >20-point absolute worsening in SALT score	Kaplan-Meier Plot	Randomized Withdrawal Population	Summary statistics will be provided at each post-baseline visit during the Long-Term extension and Bridging Long-Term Extension Period.	Other secondary
	Proportion of patients achieving SALT $\leq 20$	Descriptive	Retreated Population	Summary statistics will be provided at Weeks 12, 16, 24, and 36 of retreatment with baricitinib	Other secondary
	Percent change in SALT score	Descriptive	Retreated Population	Summary statistics will be provided at Weeks 12, 16, 24, and 36 of retreatment with baricitinib	Other secondary
PRO for Scalp Hair Assessment	Proportion of patients with a PRO for Scalp Hair Assessment score of 0 or 1	Descriptive	Retreated Population	Summary statistics will be provided at Weeks 12, 16, 24, and 36 weeks of retreatment with baricitinib	Other secondary

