**Table JAHO.4.11 Description of Primary, Secondary and Exploratory Efficacy Analyses**

Measure	Variable	Analysis Method (Section 4.2.3)	Censoring Rule	Population (Section 4.2.1)	Time Point
	Time to achieve SALT $\leq 20$	
 
Descriptive
 
Kaplan-Meier plot
 
	Secondary Censoring Rule	Retreated Population	Week 52 - 200
	Time to loss of treatment benefit (>20-point absolute worsening in SALT score)	
 
Descriptive
 
Kaplan-Meier plot
 
	Tertiary Censoring Rule	Randomized Withdrawal Population	Week 52 - 200
	Proportion of patients achieving an absolute SALT $\leq 10$	Descriptive using Obs and mLOCF	Tertiary Censoring Rule	Randomized Withdrawal Population	Weeks 52-200
		Descriptive using Obs and mLOCF	Secondary Censoring Rule	Uptitration Population	Weeks 52-200
		Descriptive using Obs	Secondary Censoring Rule	Retreated Population	Weeks 52-200
	Proportion of patients with loss of benefit in SALT	Descriptive using Obs and mLOCF	Tertiary Censoring Rule	Randomized Withdrawal Population	Weeks 52-200
	Proportion of patients without loss of benefit in SALT	Descriptive using Obs and mLOCF	Tertiary Censoring Rule	Randomized Withdrawal Population	Weeks 52-200

Measure	Variable	Analysis Method (Section 4.2.3)	Censoring Rule	Population (Section 4.2.1)	Time Point
	SALT Change and Percent Change from baseline	Descriptive using Obs and mLOCF	Tertiary Censoring Rule	Randomized Withdrawal Population	Weeks 52-200
		Descriptive using Obs and mLOCF	Secondary Censoring Rule	Uptitration Population	Weeks 52-200

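### SAP Table JAHO4.9 plots time to loss of benefit in patients selected for having lost it; the row should use the Randomized Withdrawal Population

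*SAP*

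**What the plan says.** SAP Section 4.11.1 (Long-Term Efficacy Analyses), Table JAHO4.9, lists "Time to >20-point absolute worsening in SALT score from Week 52" with the method "Kaplan-Meier Plot" and the population Retreated. The text available shows no censoring rule or time point for this row.

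Table JAHO.4.1 defines the Retreated Population as "A subset of patients who enter randomized withdrawal (randomized to placebo at Week 52") who "were retreated with their baseline baricitinib dose at any time after experiencing loss of treatment benefit". It glosses loss of benefit in brackets as a SALT score above 20.

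Two other SAP tables carry the same endpoint:
- Table JAHO.4.8: "Time to >20-point absolute worsening in SALT score", Kaplan-Meier plot, Randomized Withdrawal Population.
- Table JAHO.4.11 (final lock): "Time to loss of treatment benefit (>20-point absolute worsening in SALT score"), Kaplan-Meier plot, Randomized Withdrawal Population, tertiary censoring rule, Weeks 52 to 200.

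In Table JAHO.2.1 the endpoint belongs to the objective that compares patients kept on baricitinib with patients moved to placebo at Week 52. The separate retreatment objective lists SALT of 20 or less, percent change in SALT and the scalp PRO. It has no time-to-loss endpoint.

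**The concern.** A patient enters the Retreated Population by losing benefit and then being retreated. A curve of time to loss of benefit drawn in that group conditions on the event it is meant to describe. It cannot estimate the chance of keeping benefit after withdrawal, and it has no continued-baricitinib arm to compare with.

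The practical risk is misreading. SAP Section 4.17.3.3 ties the Week 104 lock to scientific disclosures. A published curve that drops to zero could be taken to mean that every withdrawn patient relapses.

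**Working it through.** The row states no sample size or event count, so there is no plan figure to reproduce. The check compares definitions and then illustrates the size.

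**1. Event.** Table JAHO.4.6 derives "With loss of treatment benefit in SALT from Week 52" as SALT after Week 52 minus SALT at Week 52 greater than 20. Table JAHO.2.1 uses the same >20-point definition.

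**2. Entry condition.** Footnote g to the study design figure (SAP Section 3.1.2) says withdrawn patients are retreated on a >20-point worsening. Under that trigger, entry requires the event in step 1.

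**3. The gloss.** Table JAHO.4.1 instead reads "at any time after experiencing loss of treatment benefit (SALT>20"). The two conditions differ: a move from 10 at Week 52 to 25 is a 15-point change, so it exceeds 20 as a score but is not a >20-point worsening. Because Week 52 SALT is at least 0, every >20-point worsening also gives a score above 20, but the reverse fails. Under the gloss alone, some members could lack the event.

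**4. Who is left out.** SAP Section 4.1 expects about 100 patients in randomized withdrawal, and footnote d allocates them 3:1. That gives 100 × 3/4 = 75 on baricitinib and 100 × 1/4 = 25 on placebo. None of the 75 can enter the plot, nor can any placebo patient who keeps benefit.

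**5. Illustration.** These assumptions are not in the documents: a proportion p of withdrawn patients loses benefit by Week 104, at a constant hazard from Week 52, with no dropout, and every relapser is retreated.
- Whole placebo arm: S(t) = (1 − p)^((t − 52)/52).
- Patients relapsing by Week 104: S_R(t) = [S(t) − S(104)] / [1 − S(104)].
- Example, p = 0.70, Week 76: S = 0.30^(24/52) = 0.574, so S_R = (0.574 − 0.300)/0.700 = 0.39.

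| Assumed p | Placebo arm, Weeks 64/76/88/104 | Retreated, Weeks 64/76/88/104 | Patients plotted (25 × p) |
|---|---|---|---|
| 0.50 | 0.85/0.73/0.62/0.50 | 0.70/0.45/0.24/0 | 12.5 |
| 0.70 | 0.76/0.57/0.43/0.30 | 0.65/0.39/0.19/0 | 17.5 |
| 0.90 | 0.59/0.35/0.20/0.10 | 0.54/0.27/0.11/0 | 22.5 |

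The Retreated curve ends at 0 for every p, because S(104) is subtracted from itself. In the Randomized Withdrawal Population each placebo curve recovers its assumed rate. A continued-baricitinib curve, with assumed loss of 5% or 20%, would end at 0.95 or 0.80 beside it.

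**6. Late relapsers.** If a fraction f of the plotted patients lost benefit only after Week 104, the curve stands at f at Week 104. That f reflects how far follow-up had run by the lock. It is not the probability of keeping benefit.

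**The case against.** Four points can be made for leaving the row alone.

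- **The curve is not empty.** A reader might infer that it carries no information. It does show how quickly relapsers relapsed, so the fault is the wrong quantity for the objective.
- **Zero is not guaranteed.** A reader might infer that nobody can be event-free and that the curve must reach exactly 0%. The documents do not support that. The bracketed SALT gloss admits patients without a >20-point change. Retreatment may occur at any time, and the Week 104 lock waits for the last patient, so some members may have relapsed after their own Week 104. A rule that drops remote-visit scores could also remove a triggering value. Hence to or near 0%.
- **The objective is served elsewhere.** A reader might infer that risk of relapse goes unreported. It does not: the row directly above in Table JAHO4.9 gives the proportion without loss of benefit in the Randomized Withdrawal Population to Week 104, and Tables JAHO.4.8 and JAHO.4.11 plan the time-to-event version there. SAP Section 4.11.5 makes analyses beyond Week 36 descriptive unless otherwise stated.
- **The table may be damaged in extraction.** Several cells are blank and may be merged, so the missing censoring rule and time point should not be counted as omissions. The population label, however, is printed in this row.

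These points limit the consequence but do not justify the label. A deliberate look at worsening after retreatment would not start its clock at Week 52. Nor does Table JAHO.4.8 settle the matter: Section 4.11.5 defers its detail to a later SAP version, and the revision history lists Table JAHO4.9 among the Version 5 updates. A programmer would follow Table JAHO4.9.

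**Conclusion.** The row is wrong as written and inconsistent with two other tables in the same SAP. Under the >20-point trigger, essentially all plotted patients have the event, and the end of the curve says nothing about the true relapse rate. In the illustration the gap at Week 104 from the full placebo arm is 0.10 to 0.50. It becomes an error only if the conditional curve is read as retention of benefit after withdrawal. The count of about 12 to 23 plotted patients assumes 50% to 90% relapse and retreatment of every relapser; a patient who relapsed and left before retreatment would not be plotted.

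The effect is confined to one descriptive figure at the Week 104 lock of the main randomized study. The primary endpoint and its inference are untouched. The open-label addendum is also unaffected, since treatment withdrawal is not among its objectives.

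**What to change.** - In Table JAHO4.9, change this row's population to the Randomized Withdrawal Population and present it by Week 52 randomized arm.
- State the Week 52 to 104 span and the tertiary plus rule, as the neighbouring Table JAHO4.9 rows do. This will not match the other two tables exactly: Table JAHO.4.8 has no censoring column, and Table JAHO.4.11 uses the tertiary rule, which keeps remote-visit data, over Weeks 52 to 200. A footnote should note the difference.
- Reconcile the bracketed gloss in Table JAHO.4.1 with the >20-point definition in Table JAHO.2.1, Table JAHO.4.6 and footnote g. I take no position on which should govern retreatment.
- If a Week 104 figure was produced as written, rerun it or label it as conditional on relapse.

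The cost is one population cell, a footnote, one reconciled definition and at most one rerun figure. No new data are needed.
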